1. INTRODUCTION

Birth defects are the main cause of fetal death, infant mortality, and morbidity worldwide. The protective effect of sufficient folic acid supplementations on several birth defects is well-established¹⁻³. However, most women failed to achieve the optimal folate status from diet alone⁴. We assume that achieving recommended folate levels before pregnancy through awareness of insufficient status and timely initiation of folic acid supplementation, based on the current red blood cell (RBC) folate status and genetic background of women of reproductive age, will exert an effect on primary prevention of both fetus and birth defects.

The FOID study is a single-blind, two-arm cluster-randomized controlled trial which conducted in Shanghai and Jiangsu Kunshan city, China⁵. This trial aims to evaluate the effectiveness of a comprehensive folate-oriented tertiary interventions (before pregnancy, during pregnancy and after delivery) embedded in the current routine primary care system in reducing the incidence of fetus and birth defects among a preparing-for-pregnancy population. The control arm will receive the current routine standard antenatal care interventions before pregnancy, while the experimental arm will additionally receive a folate-oriented tertiary intervention based on this. Before conception, the participants in the experimental arm will receive an RBC folate concentration test at enrollment, and those with insufficient levels (<400ng/mL) will receive a phone interview with an instruction of folic acid supplementation to improve their folate status to the target level before pregnancy based on a second RBC folate examination. During pregnancy, pregnancies with positive tests in the routine nuchal translucency (NT) screen at early gestation, ultrasound screening in mid-gestation will be referred to the authorized tertiary hospital for counseling according to their genetic and prenatal diagnosis of the fetal defect(s). After delivery, newborns with fetus and birth defect(s) will be referred to a clinical team at the authorized tertiary pediatric hospital for treatment and follow-up. The current pragmatic cluster randomized trial will provide real-world evidence on the necessity and effectiveness of preconception intervention focusing on achieving sufficient folate nutrition levels in prevention of

fetal and birth defects.

The purpose of this Statistical Analysis Plan is to define the outcome variables, statistical methods, and analysis strategies to address the objectives of the FOID study.

2. STUDY OBJECTIVES AND OUTCOMES

2.1. Study Objectives

2.1.1. Primary objective

The primary objective is to evaluate the effectiveness of community-based folate-oriented tertiary interventions focusing on achieving sufficient RBC folate levels before conception among pregnant-planning women on the incidence of fetus and birth defects.

2.1.2. Secondary objectives

The secondary objectives include to determine the effectiveness of the experimental interventions compared with the routine primary care on the following outcomes: (1) the incidence rate of fetus defects, birth defects, spontaneous pregnancy loss (including miscarriages and artificial abortions) and stillbirths related to all kinds of congenital defects; (2) the incidence of infant death or severe organ dysfunctions; and (3) prevalence of maternal gestational complications, including gestational diabetes, hypertension, and preeclampsia; (4) the medical costs related to fetus and birth defects during pregnancy and after birth.

2.2. Outcomes

2.2.1. Primary outcome

The primary outcome is the occurrence of fetus defects, stillbirth, and neonatal birth defects identified from the confirmation of pregnancy to 28 days after birth.

- **Description:**

This is a composite outcome that includes a total of 24 types of defects according to the national birth defects surveillance policy, including fetus defects detected by

screening examinations for Down syndrome (DS), NT during early gestation, organ defects identified by routine antenatal ultrasound image examinations during the second trimester, stillbirth occurring during the entire gestation period, and birth defects identified after delivery and diagnosed by clinical examinations including ultrasound examination (Details of 24 defects types see Appendix 1). The primary outcome will be defined as “occurred” if any one of the 24 defects occurs. All examinations to measure the primary outcome will follow current routine protocols. Besides, detailed information on both miscarriages and artificial abortions will be collected, including the time of abortion, reasons for abortion, and antenatal information before an abortion.

- Time Frame: from the confirmation of pregnancy to 28 days after birth.
- Type: binary variable (Yes / No).

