2.2.2. Secondary outcomes

(1) The occurrence of fetus defects

- This is a composite outcome and will be defined as “occurred” if any of the 24 defects are detected by routine ultrasound screening during pregnancy (Details of defects types see Appendix 1).
- Time Frame: from the confirmation of pregnancy to before delivery.
- Type: binary variable (Yes / No).

(2) The occurrence of birth defects

- This is a composite outcome and will be defined as “occurred” if any of the 24 defects are detected by ultrasound examination within one year old (Details of defects types see Appendix 1).
- Time Frame: from birth to one year old.
- Type: binary variable (Yes / No).

(3) The occurrence of infant death or severe organ dysfunctions

- This is a composite outcome and will be defined as “occurred” if either infant death or severe organ dysfunctions occur.
- Time Frame: from birth to 6 months after delivery (can be expanding to the end of the 7th month).
- Type: binary variable (Yes / No).

(4) The occurrence of abortion that related with congenital defects

- Time Frame: from the confirmation of pregnancy to the 28th gestational week.
- Type: binary variable (Yes / No).

(5) Count of fetus defects, stillbirth, and birth defects

- Time Frame: from the confirmation of pregnancy to 28 days after birth.
- Type: Count-Number of events.

(6) Occurrence of confirmed congenital heart defects (CHD)

- All pregnancies will have prenatal ultrasound scans in the second trimester (around 20 to 24 weeks of gestation) performed by trained ultrasound sonographers; abnormal findings will be confirmed by authorized tertiary fetal medical centers. All newborns will have routine neonatal CHD screening, and those screened positive will be subsequently sent for further echocardiographic confirmation. The nomenclature of the International Paediatric and Congenital Cardiac Code (of the Nomenclature Working Group of the International Society for Nomenclature of Paediatric and Congenital Heart Disease) will be used to define CHD.
- Time Frame: from the confirmation of pregnancy to 28 days after birth.
- Type: binary variable (Yes / No).

(7) Occurrence of maternal gestational diabetes (GDM)

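### The event rule for the primary outcome names only the 24 listed defects, while the sample size, the primary analysis and Table 3 also count stillbirth

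*SAP*

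**What the plan says.** Section 2.2.1 opens by naming three components of the primary outcome (fetal defects, stillbirth and neonatal birth defects), "identified from the confirmation of pregnancy to 28 days after birth". Its description presents a composite of 24 defect types and, within the same sentence, mentions "stillbirth occurring during the entire gestation period". The next sentence, the only one that says when the outcome counts as having happened, scores it "if any one of the 24 defects occurs".

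Appendix 1 gives 23 named malformations or syndromes and a 24th category for others. Stillbirth is not on the list.

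Stillbirth is a separate component in 2.2.2(5), 3.5, 5.1.1 and Table 3. On early losses, 2.2.3 defines abortion so that it includes miscarriage, and the defect-related abortion outcome in 2.2.2(4) runs "from the confirmation of pregnancy to the 28th gestational week". Sections 2.2.3 and 5.1.1 open the window at 12 gestational weeks.

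**The concern.** The primary variable is a single yes/no per woman, and 5.1.1 draws the main conclusion from it. If the derivation rule and the analysis section disagree on what scores yes, two programmers working from the same SAP can produce different primary datasets. Section 3.4 has the programs written blind on dummy codes, so the derivation must be unambiguous at that stage. None of the sensitivity analyses in 5.1.2 varies the outcome definition. If the question were settled after unblinding, the choice of endpoint could depend on the data.

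**Working it through.** **1. Who is an event under which text**

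| Woman's outcome | Literal 2.2.1 rule | 5.1.1 |
|---|---|---|
| Listed defect found after week 12 | event | event |
| Stillbirth with a listed defect, after week 12 | event | event |
| Stillbirth, no recorded defect | non-event | event |
| Spontaneous loss between weeks 12 and 28, no listed defect | non-event | event if called stillbirth, non-event if called miscarriage |
| Listed defect found, or loss, after confirmation of pregnancy but before week 12 | defect: event; loss without defect: non-event | outside the window |

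Rows 3 to 5 are where the text fails. In row 4 the SAP gives neither a boundary week nor a precedence rule. A loss with a listed defect is an event either way, provided that it falls inside the window. Row 5 turns on the window start; 2.2.3 schedules NT from week 11, so a finding in that week is inside one window and outside the other.

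**2. Can the 24 defects be read as covering stillbirth?** Nearly the same phrase defines two defects-only secondary outcomes: 2.2.2(1), "if any of the 24 defects are detected by routine ultrasound screening during pregnancy", and 2.2.2(2), "if any of the 24 defects are detected by ultrasound examination within one year old". If the phrase covered stillbirth in 2.2.1, it would be expected to do so there too. Appendix 1 does not place stillbirth under its last category.

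**3. Illustration of size**

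Inputs from 3.5: p0 = 0.08, p1 = 0.04, m = 100 per centre, k = 0.23, 85% power, 5% type I error (two-sided assumed), 11 clusters per arm.

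V = p0(1−p0)/m + p1(1−p1)/m + k²(p0² + p1²) = 0.000736 + 0.000384 + 0.000423 = 0.001543.

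Clusters per arm = a + (1.960 + 1.036)² × V/(p0−p1)² = a + 8.978 × 0.001543/0.0016 = a + 8.66.

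- a = 1: 9.66, so 10 per arm; power with 11 per arm is 89.6%.
- a = 2: 10.66, so 11 per arm, the SAP's 22 in total; power with 11 per arm is 86.3%.

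Other variants also give 11 per arm (t quantiles with a = 1, or 90 evaluable women per centre), so a = 2 is not the only route to 22. The planned size is reproduced and is not in question.

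Now let s be the part of the 8% control rate that is stillbirth without a recorded defect. The SAP does not give s; 0.5, 1 and 2 points are assumptions. Power = Φ(√[(11−a)(p0−p1)²/V] − 1.96). Each power cell shows a = 1, then a = 2.

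| s | Control events affected (1,100 × s, of 88) | Defects only, halved: power (RR 0.50) | Stillbirth counted but unaffected: RR | Power |
|---|---|---|---|---|
| 0.5 points | 5.5 | 88.1%, 84.6% | 0.53 | 84.8%, 80.9% |
| 1 point | 11 | 86.3%, 82.6% | 0.56 | 78.7%, 74.4% |
| 2 points | 22 | 81.8%, 77.7% | 0.625 | 63.8%, 59.3% |

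Example for s = 1 point: experimental risk = 0.07/2 + 0.01 = 0.045, and 0.045/0.08 = 0.5625.

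If stillbirth is halved as well, the RR is 0.50 under both definitions, and leaving stillbirth out lowers power from the base (89.6% or 86.3%) to the defects-only column. The direction of the power change thus depends on an effect that the SAP does not state.

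**The case against.** The best defence is that one reading dominates. The sentence just before the rule puts stillbirth inside the composite, so the rule can be taken as loose shorthand for that list, and 5.1.1, from which an analyst would program, is clear. This stands as evidence of the likely intention and as the reason for the default fix. It does not remove the contradiction, since the shorthand carries a defects-only meaning elsewhere in 2.2.2.

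A definition of stillbirth may also sit in the protocol, which is not at hand. That is fair, and the missing threshold is not faulted as an omission. The fault is that 2.2.1 extends stillbirth over all of gestation while 2.2.3 assigns miscarriage to abortion.

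Several stronger readings are tempting, and the SAP does not support them:

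- *Everything else in the SAP counts stillbirth.* It does not. The primary objective speaks only of an effect "on the incidence of fetus and birth defects", and the introduction, 2.2.3(1) and 3.1 likewise name only defects.
- *Section 2.1.2 gives a rival primary definition.* Its phrase "stillbirths related to all kinds of congenital defects" belongs to a secondary objective. It shows that a narrower intention is conceivable, no more.
- *Every loss before week 28 is ambiguous for the primary outcome.* Apart from the window question, only losses without a listed defect are.
- *The trial is underpowered.* The low figures need an assumed share. At 2 points, a quarter of control events (22 of 88) would be defect-free stillbirths, for which the SAP gives no support.
- *Neonatal heart screening differed by arm.* The Birth row of the 3.3 table shows it only in the experimental column, but 2.2.2(6) gives it to all newborns and 3.1 has the same outcome routines in both arms. This is probably a table slip.

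**Conclusion.** Wrong as written, and to be fixed before unblinding. Applied literally, the 2.2.1 rule drops a component that the sample size, the primary analysis and Table 3 all include. This conclusion rests on the text alone and on no assumption about rates.

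The effect on the result cannot be determined from the SAP. Every RR and power figure above is an illustration under an assumed stillbirth share, a two-sided test and a choice of formula variant. The two window starts are a smaller inconsistency in the same definition. The 3.3 table row is a separate, minor point.

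**What to change.** Before database lock and unblinding:

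1. Change the 2.2.1 event rule to any of the 24 defects or a stillbirth, in line with 3.5, 5.1.1 and Table 3. If the sponsor intends only defect-related stillbirths, change those sections, the opening of 2.2.1 and 2.2.2(5) instead.
2. State how a loss before week 28 without a listed defect is classified. The boundary is for the sponsor to set. Align the whole-gestation wording in 2.2.1 with it.
3. Use one window start in 2.2.1, 2.2.2(5), 2.2.2(6), 2.2.3 and 5.1.1. If 12 weeks is kept, say how week-11 NT findings and earlier losses are handled.
4. Report stillbirths with and without a recorded defect by arm, and run one sensitivity analysis under the definition not chosen.
5. As a minor item, reconcile the Birth row of the 3.3 table with 2.2.2(6) and 3.1.

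The cost is SAP wording, one extra model run and one descriptive addition to a table. Appendix 2.2 already holds gestational week at delivery and birth defect records. Neither Appendix 2.1 nor 2.2 shows a field named stillbirth for the index pregnancy, so its source record should be confirmed.

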2.2.2. Secondary outcomes

(1) The occurrence of fetus defects

- This is a composite outcome and will be defined as “occurred” if any of the 24 defects are detected by routine ultrasound screening during pregnancy (Details of defects types see Appendix 1).
- Time Frame: from the confirmation of pregnancy to before delivery.
- Type: binary variable (Yes / No).

(2) The occurrence of birth defects

- This is a composite outcome and will be defined as “occurred” if any of the 24 defects are detected by ultrasound examination within one year old (Details of defects types see Appendix 1).
- Time Frame: from birth to one year old.
- Type: binary variable (Yes / No).

(3) The occurrence of infant death or severe organ dysfunctions

- This is a composite outcome and will be defined as “occurred” if either infant death or severe organ dysfunctions occur.
- Time Frame: from birth to 6 months after delivery (can be expanding to the end of the 7th month).
- Type: binary variable (Yes / No).

(4) The occurrence of abortion that related with congenital defects

- Time Frame: from the confirmation of pregnancy to the 28th gestational week.
- Type: binary variable (Yes / No).

(5) Count of fetus defects, stillbirth, and birth defects

- Time Frame: from the confirmation of pregnancy to 28 days after birth.
- Type: Count-Number of events.

(6) Occurrence of confirmed congenital heart defects (CHD)

- All pregnancies will have prenatal ultrasound scans in the second trimester (around 20 to 24 weeks of gestation) performed by trained ultrasound sonographers; abnormal findings will be confirmed by authorized tertiary fetal medical centers. All newborns will have routine neonatal CHD screening, and those screened positive will be subsequently sent for further echocardiographic confirmation. The nomenclature of the International Paediatric and Congenital Cardiac Code (of the Nomenclature Working Group of the International Society for Nomenclature of Paediatric and Congenital Heart Disease) will be used to define CHD.
- Time Frame: from the confirmation of pregnancy to 28 days after birth.
- Type: binary variable (Yes / No).

(7) Occurrence of maternal gestational diabetes (GDM)

- Pregnant participants will receive a 75-g oral glucose tolerance test during 24-28 gestational weeks, and GDM will be diagnosed if any of the following criteria are met, based on the recommendations of the International Association of the Diabetes and Pregnancy Study Groups Consensus Panel: fasting glucose ≥ 5.1 mmol/L, 1-hour glucose ≥ 10.0 mmol/L, or 2-hour glucose ≥ 8.5 mmol/L.
- Time Frame: during 24-28 gestational weeks.
- Type: binary variable (Yes / No).

(8) Maternal gestational weight gain (kg)

- This outcome will be calculated as body weight at delivery minus weight before pregnancy (self-reported).
- Time Frame: from pre pregnancy to delivery.
- Type: continuous variable.

(9) Maternal weight gain (kg) at early gestation

- This outcome will be calculated as body weight at around 20 gestational weeks minus weight before pregnancy (self-reported).
- Time Frame: from pre pregnancy to 20 gestational weeks.
- Type: continuous variable.

(10) Occurrence of gestational hypertension

- Pregnant participants will undergo blood pressure measurements at each prenatal visit. Gestational hypertension will be diagnosed if systolic blood pressure ≥ 140 and/or diastolic blood pressure ≥ 90 mmHg, based on the recommendations of the International Society for the Study of Hypertension in Pregnancy (ISSHP).
- Time Frame: during pregnancy.
- Type: binary variable (Yes / No).

- (11) Maternal body weight (kg) at 6 months after delivery (Continuous variable)
- (12) Maternal HbA1c (%) at 6 months after delivery (Continuous variable)
- (13) Infant body weight (g) at birth, 42 day, 3 months, and 6 months (Continuous, repeated measurements)
- (14) Infant length (cm) at birth, 42 day, 3 months, and 6 months (Continuous, repeated measurements)
- (15) Infant body mass index (kg/m²) at birth, 42 day, 3 months, and 6 months (Continuous, repeated measurements)
- (16) Medical cost that relates with fetus and birth defects during pregnancy and after birth (Time Frame: from confirmation of pregnancy to one year old after birth) (Continuous variable)

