2.2.3. Case ascertainment and case definitions

(1) Fetus and Birth defects

The examinations for detecting fetus and birth defects will follow the national routine usual care protocols. All fetus and birth defects identified from the 12 gestational weeks to 28 days after birth will be included. In consistent with the national birth defects surveillance policy, a total of 24 types of defects are defined (details of types of defects types see Appendix 1). Fetus defects will be detected by routine screening programs including prenatal DS screening, NT examination during gestational week 11 to 15, and ultrasound image examination during the second trimester (18-20 gestational week); and the number and type of birth defects after childbirth will be diagnosed and recorded according to national routine professional clinical examinations.

DS, caused by the trisomy, translocation, or partial trisomy of chromosome 21, is the most common genetic cause of intellectual disability. DS will be diagnosed by neonatologist. Neural tube defects including spina bifida and hypospadias, will be diagnosed by ultrasound examination and pediatric neurosurgeon.

CHD will be diagnosed by echocardiographic confirmation based on the local CHD screening policy (pulse oximetry plus cardiac murmurs). Hydrocephalus, digestive tract malformations, urinary malformations and other defects also will also be diagnosed either by ultrasound or some other specific diagnosis methods. From June 2016, a neonatal congenital heart defects screening policy has been issued in Shanghai city, the screening and diagnosis of CHD in neonates is embedded in this program following the routine protocols.

(2) *Abortion*

Abortion is defined as pregnancy suspension including miscarriage and artificial abortion. Detailed information for abortions will be collected, including time of abortion, reasons for abortion especially and antenatal information before abortion.

(3) *Pregnancy complications*

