9. APPENDIXES

9.1. Appendix 1. Types of fetus defects and birth defects

1. Anencephalus
2. Spina bifida
3. Encephalocele
4. Congenital Hydrocephalus
5. Cleft Palate
6. Cleft Lip
7. Cleft Lip with Cleft Palate
8. Microtia (including Anotia)
9. Deformity of external ear(s) (except Microtia and Anotia)
10. Esophageal atresia or stenosis
11. Anorectal atresia (including Congenital Anorectal Malformations)
12. Hypospadias
13. Ectopocystis
14. Pes Equinovarus
15. Polydactylism
16. Syndactylia
17. Limb shortening
18. Congenital Diaphragmatic Hernia
19. Peromphalus
20. Celoschisis
21. Conjoined Twins
22. Trisomy 21 syndrome
23. Congenital heart disease
24. Others.

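### Secondary outcomes (1) and (2) count only defects found by ultrasound, although the primary outcome and the case definitions in SAP 2.2.3 accept other routes; trisomy 21 found only through Down syndrome screening is therefore missed in (1)

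*SAP*

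**What the plan says.** SAP 2.2.2 (1) treats a fetus defect as having occurred if "any of the 24 defects are detected by routine ultrasound screening during pregnancy", over the period "from the confirmation of pregnancy to before delivery". It refers to the full list in Appendix 1, where item 22 is "Trisomy 21 syndrome".

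Two other sections give fetus defects a wider rule:

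- SAP 2.2.1 (primary outcome) lists these prenatal sources: "screening examinations for Down syndrome (DS), NT during early gestation, organ defects identified by routine antenatal ultrasound image examinations during the second trimester".
- SAP 2.2.3 (case definitions) states: "Fetus defects will be detected by routine screening programs including prenatal DS screening, NT examination during gestational week 11 to 15", and then adds the second-trimester ultrasound.

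Outcome (2) in 2.2.2, birth defects up to one year of age, likewise requires detection by ultrasound examination. For the same kind of event, 2.2.3 says that defects after childbirth are diagnosed and recorded through routine clinical examination, and that "DS will be diagnosed by neonatologist".

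**The concern.** One term has two ascertainment rules in the same plan. Table 3 has a row for fetal defects and a row for birth defects, both filled from the outcome definitions. A programmer working from 2.2.2 and one working from 2.2.3 could put different counts in the same row, and nothing in the SAP says which section governs.

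The narrow rule also undercuts itself. It refers to all 24 types and then sets a detection condition that a case found only by DS screening cannot meet. Secondary objective (1) in 2.1.2 names fetus defects without any ultrasound limit, so nothing suggests that an ultrasound-only outcome was intended. At stake are the correctness of two reported secondary outcomes and the reader's ability to relate them to the primary result.

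**Working it through.** There is no stated figure to reproduce, because the point concerns definitions. The check compares the definitions and then works out the direction of any error.

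**1. Prenatal routes accepted, by section**

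- SAP 2.2.1, primary outcome: DS screening, NT, second-trimester ultrasound.
- SAP 2.2.3, case definitions: DS screening, NT, second-trimester ultrasound.
- SAP 2.2.2 (1): routine ultrasound screening only.

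**2. Following cases through the rules**

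- *Trisomy 21 found by DS screening, no listed defect on ultrasound, pregnancy terminated.* Event in the primary outcome: yes, because DS screening is a named route and trisomy 21 is on the list. Event in outcome (1): no. Event in outcome (2): no, because its window opens at birth.
- *Trisomy 21 with a listed structural defect seen on ultrasound.* Event in both the primary outcome and outcome (1).
- *Case found at the NT examination.* Event in the primary outcome. For outcome (1) the answer is open. The clause says ultrasound during pregnancy and the window starts at confirmation of pregnancy, so an NT scan could be included. Yet the SAP repeatedly names NT apart from ultrasound, as in the Introduction: "positive tests in the routine nuchal translucency (NT) screen at early gestation, ultrasound screening in mid-gestation".
- *Live-born infant with trisomy 21 diagnosed by the neonatologist, no ultrasound finding.* A diagnosed case under 2.2.3, but not an event in outcome (2) read literally. The same holds for any listed defect recognised by clinical examination without ultrasound. SAP 2.2.1 treats ultrasound as only one of the clinical examinations that diagnose birth defects.

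**3. Direction of the error in outcome (1)**

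Let p_E and p_C be the risks in the experimental and control arms under the wide rule. Let s_E and s_C be the shares of those events that the ultrasound clause omits.

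- Reported risks: p_E(1 − s_E) and p_C(1 − s_C). Each is too low whenever its share is above zero.
- Reported risk ratio: (p_E/p_C) × (1 − s_E)/(1 − s_C). It equals the wide-rule ratio if s_E = s_C and departs from it otherwise.
- Reported risk difference: p_E(1 − s_E) − p_C(1 − s_C). With a common share s this is (1 − s)(p_E − p_C), so it shrinks towards zero by that share. With unequal shares it can move either way.

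The SAP gives no rate of trisomy 21 and no count of defects by route of detection, so s_E and s_C cannot be derived. Unequal shares are possible in principle. If the intervention lowered structural defects but not trisomy 21 (a hypothetical, not a statement in the SAP), s_E would exceed s_C and the reported ratio would look more favourable than the wide-rule ratio.

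**The case against.** The best defence is that ultrasound is loose shorthand in 2.2.2. Both (1) and (2) use it while citing all 24 types, and 2.2.3 is the section that carries the case definitions, so the analysts may well apply the wider rule. That is plausible. But the SAP never says that 2.2.3 overrides 2.2.2, and an outcome definition should not depend on the reader guessing so.

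Several stronger readings are tempting and should not be drawn:

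- *That outcomes (1) and (2) were meant to add up to the primary composite.* The SAP does not say this, and they could not. Stillbirth is in the composite but in neither outcome, and outcome (2) runs to one year while the composite stops at 28 days. A defect seen before and after birth could also count in both.
- *That all prenatally identified trisomy 21 is lost.* Only cases without a listed defect on ultrasound are affected, and the exclusion is firm only for the DS-screening route.
- *That such a case disappears from the secondary outcomes.* Outcome (4), abortion related to congenital defects, can capture it up to week 28. Outcome (5), the count of events, has no ultrasound condition. Neither corrects the count in outcome (1).
- *That a percentage can be put on the loss.* Nothing in the SAP supports one.

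It is also fair to note that 2.2.3 is itself incomplete. It assigns the diagnosis of DS to a neonatologist and gives no prenatal criterion. The statement that a terminated case counts in the primary outcome therefore rests on 2.2.1 and on the DS-screening route in 2.2.3.

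**Conclusion.** The inconsistency stands. Outcome (1) has a narrower rule than the primary outcome and 2.2.3 for the same term, and outcome (2) conflicts with the postnatal routes in 2.2.3. Applied as written, outcome (1) omits trisomy 21 found only through DS screening, and outcome (2) omits listed defects diagnosed without ultrasound. The size is unknown and cannot be obtained from the SAP. The absolute risks for outcome (1) are understated, and the risk ratio, which is the planned effect measure for binary secondary outcomes in 5.2.1, is affected only if the omitted shares differ between arms.

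The primary analysis and the main conclusion are not touched. This is worth correcting, but it is a definitional repair to two of 16 secondary outcomes and does not threaten the trial. The conclusion assumes that 2.2.2 is applied literally; if the analysts already use 2.2.3, the counts are right and only the text is wrong.

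**What to change.** - **Outcome (1):** define it as any of the 24 types identified before delivery by any route listed in 2.2.3 (DS screening, NT examination or ultrasound), and apply the same confirmation standard as in the primary outcome. If an ultrasound-only outcome is truly wanted, say so and rename it in 2.2.2 and Table 3.
- **Outcome (2):** replace the ultrasound condition with the postnatal diagnostic routes of 2.2.3.
- **2.2.3:** state how trisomy 21 identified before birth is established as a case, since only the neonatologist's diagnosis is mentioned.

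The cost is a few clauses of wording. On data, Appendix 2.1 has a free-text birth-defect diagnosis field under pregnancy, but neither Appendix 2.1 nor 2.2 lists a field for a DS-screening or NT result. The primary outcome already needs these cases from the medical records, so the change asks for nothing beyond that. Before database lock, the team should still confirm that the free-text field and those records identify cases found by DS screening.

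### Secondary outcome (2), birth defects, names ultrasound as its only route of detection, which conflicts with SAP 2.2.1 and 2.2.3 and, read literally, drops defects on the trial's own list

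*SAP*

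**What the plan says.** Section 2.2.2(2) makes birth defects a yes/no composite that has occurred if "any of the 24 defects are detected by ultrasound examination within one year old". It points to Appendix 1 for the list and sets "Time Frame: from birth to one year old".

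Other parts of the SAP describe postnatal ascertainment more widely:

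- Section 2.2.1 (primary outcome) includes "birth defects identified after delivery and diagnosed by clinical examinations including ultrasound examination".
- Section 2.2.3 (case definitions) says that "the number and type of birth defects after childbirth will be diagnosed and recorded according to national routine professional clinical examinations". It adds that "DS will be diagnosed by neonatologist", and that hydrocephalus, digestive tract, urinary and other defects are "diagnosed either by ultrasound or some other specific diagnosis methods".
- Section 3.4 names neonatologists, as well as the ultrasound department, as observers of the outcome, with outcome data taken from medical records.
- Appendix 1 lists trisomy 21 (item 22) and external defects such as "15. Polydactylism".

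The window also differs. Section 2.2.3 states: "All fetus and birth defects identified from the 12 gestational weeks to 28 days after birth will be included".

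**The concern.** The sentence in 2.2.2(2) is the event rule that a programmer would code. It admits one detection route, while the case definitions admit several. Two analysts working from the same SAP could therefore build two different variables, one from 2.2.2(2) and one from 2.2.3, and each could cite the text in support.

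The outcome is not incidental. It serves secondary objective (1), is analysed under 5.2.1 and has its own row in Table 3 with a risk ratio and p-value. If the narrow version were used, the result labelled birth defects would describe only infants with a defect picked up on ultrasound. It would also sit beside a primary composite that applies a wider rule to the same newborns.

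**Working it through.** The SAP states no figure on this point, so the check is a comparison of text followed by a trace of individual cases.

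**Detection rule and window, side by side**

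| Place in SAP | Postnatal detection rule | Window |
|---|---|---|
| 2.2.1 primary outcome | Clinical examinations, ultrasound being one | To 28 days after birth |
| 2.2.2(2) birth defects | Ultrasound; nothing else named | Birth to one year |
| 2.2.3 case definitions | Routine clinical examinations; neonatologist for Down syndrome; ultrasound or another specific method for others | 12 gestational weeks to 28 days after birth |
| 3.4 observers | Ultrasound department and neonatologists | Not stated |

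**Cases traced through the literal wording**

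1. *Trisomy 21, diagnosed by the neonatologist by day 28, no defect seen on ultrasound.* It is on the list, a case under 2.2.3 and an event for the primary outcome. Under 2.2.2(2) it is not an event. The SAP alone establishes this conflict, because 2.2.3 itself names a diagnostician outside ultrasound.
2. *Polydactyly seen on newborn examination by day 28.* It is on the list and an event for the primary outcome, but not an event under 2.2.2(2). That such a defect is found by inspection is general knowledge, though the clinical-examination wording in 2.2.1 and 2.2.3 fits it.
3. *Congenital heart disease confirmed by echocardiography.* Echocardiography is an ultrasound method, so the case counts under every rule. There is no conflict.
4. *Spina bifida or hypospadias.* Section 2.2.3 assigns both to ultrasound together with a specialist, so as the SAP is written these do not show the conflict.
5. *A listed defect first found after day 28 but before one year.* It falls inside the 2.2.2(2) time frame and outside the 2.2.3 window. This holds whatever the detection route.

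**Size**

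Let s be the share of infants with a listed birth defect in whom no defect was detected by ultrasound. The literal rule then counts (1 − s) of the infants that the wider rule would count. With shares s_E in the experimental arm and s_C in the control arm, the literal risk ratio equals the wider-rule risk ratio multiplied by (1 − s_E)/(1 − s_C). The SAP supplies none of these shares. It gives no frequency by defect type or detection route, and no expected rate for this outcome. The 8% and 4% in 3.5 belong to the primary composite. Counting entries in Appendix 1 does not help, because entries are types and not cases.

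**Data items**

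Appendix 2.1 has a text field for birth defect diagnosis. Appendix 2.2 has one for birth defect records, in the delivery block and drawn from the maternal antenatal record system. No listed item flags postnatal detection by ultrasound, and none clearly carries defects found between delivery and one year.

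**The case against.** The best defence is loose drafting. Section 2.2.2(2) does not contain the word only. It refers to all 24 types and to an appendix that includes trisomy 21 and polydactyly, so an ultrasound-only reading works against the sentence's own scope. Section 2.2.3 is the fuller definition, and no variable in Appendix 2 would readily support an ultrasound-only count. A broad intention is therefore plausible. What remains is that nothing in 2.2.2(2) admits another route, and the SAP does not say which section prevails.

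Three stronger readings are tempting, and the SAP does not support them:

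- *That the outcome loses a large or quantifiable part of its events and precision.* No shares are given, so any percentage would be invented. Heart defects, and others detected by ultrasound, still count.
- *That the outcome cannot be squared with the primary composite.* The two were never nested. The primary includes fetal defects and stillbirth and stops at 28 days, whereas this outcome starts at birth and runs to one year. Different counts are expected under any detection rule. The conflict is confined to the route.
- *That the rule biases the comparison between arms.* The table in 3.3 puts neonatal heart screening with echocardiography in the experimental column and recording of observed defects in the control column. However, 2.2.2(6) says that all newborns are screened, and 3.1 says that outcomes are measured by the same routines in both arms. Unequal imaging is a possibility, not something the SAP establishes.

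**Conclusion.** The inconsistency is real and should be corrected before analysis. As written, 2.2.2(2) would exclude listed defects that 2.2.1 and 2.2.3 count. Down syndrome is the clearest case, and external defects such as polydactyly are a further example resting on general knowledge of how they are found.

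The effect on event numbers, precision or the risk ratio is unknown and cannot be derived from the SAP. The conclusion depends only on the wording being applied literally. If the broad reading was intended, the correction records that intention and changes nothing else. The problem touches one secondary outcome, and the primary analysis and main conclusion are unaffected. The mismatch between one year and 28 days is a second defect in the same definition and belongs in the same edit.

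**What to change.** Replace the detection clause in 2.2.2(2) with wording to this effect: *any of the 24 Appendix 1 types diagnosed after birth by any routine route (clinical examination, ultrasound, echocardiography or other specific diagnostic method), applied identically in both arms.*

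In the same edit:

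- Reconcile the one-year time frame in 2.2.2(2) with the 28-day window in 2.2.3, either by limiting the 2.2.3 window to the primary outcome or by changing one of the two. Check the choice against 4.2, which closes the analysis once the last participant has completed primary-outcome follow-up and six months of age.
- State the data source for defects found after the delivery record. The birth defect field in Appendix 2.2 covers delivery and does not by itself show ascertainment to one year.

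The rewording costs one sentence. Settling the window and source takes a decision and a line or two more. If no source exists for defects found after delivery, the time frame has to be set to what the records can support.
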